1 INTRODUCTION

1.1 Disease and Study Treatment Review

RPL554, a small molecule isoquinolone derivative, is a dual inhibitor of two isoforms (type 3 and 4) of the phosphodiesterase (PDE) family of enzymes. PDE3 and PDE4 are known to have a role in modulating the inflammatory airway response in respiratory diseases, including chronic obstructive pulmonary disease (COPD), allergic asthma and allergic rhinitis. In general, PDE3 inhibitors act as bronchodilators (through interaction with smooth muscle cells), whilst PDE4 inhibitors have anti-inflammatory properties and there is also evidence to suggest that combined inhibition of PDE3 and PDE4 can have additive or synergistic anti-inflammatory and bronchodilator effects (reviewed by Abbott-Banner & Page, 2014). Pharmacological evidence from pre-clinical experiments with dual PDE3/4 inhibitors suggests that RPL554 may have potential therapeutic activity in allergic asthma, COPD, cystic fibrosis and allergic rhinitis.

PDE4 inhibitors (administered orally) have exhibited anti-inflammatory actions; however, they have been associated with unfavourable gastrointestinal side effects such as nausea, emesis, diarrhoea, abdominal pain, loss of appetite and weight loss (Harbinson et al, 1997; van Schalkwyk et al, 2005; Compton et al, 2001; Rabe et al, 2005; Rennard et al, 2006; Calverley et al, 2007; Gamble et al, 2003; Grootendorst et al, 2007). Dual PDE3/PDE4 inhibitors (administered by inhalation) have exhibited both bronchodilator and anti-inflammatory actions, with a more favourable side effect profile (Ukena et al, 1995). It is plausible that increased efficacy with reduced side effects may be achievable with administration of a dual PDE3/4 inhibitors. It has also been demonstrated in tracheal ring preparations that RPL554 causes a synergistic bronchodilator effect when added to antimuscarinic agents, as well as additive properties with beta₂.agonists (Calzetta et al, 2013; Calzetta et al, 2015).

The safety, bronchodilator, bronchoprotective and anti-inflammatory activities of RPL554 have been evaluated in five completed studies in healthy subjects, patients with mild-moderate persistent asthma and those with allergic rhinitis and COPD, using a nebulised solution of RPL554 in citrate/phosphate buffered saline at pH 3.2 (Franciosi et al, 2013; summarised in Investigator Brochure). Systemic exposure following inhalation using this solution formulation was low and somewhat variable, with maximum concentration (C_{max}) values ranging from about 0.9 ng/mL following administration at 0.018 mg/kg to about 4 ng/mL at 0.072 mg/kg. Area under the curve (AUC)_{0-t} values ranged from about 1.5 ng.h/mL to 11 ng.h/mL over the same dose range. Mean half-life values ranged from approximately 3 to 7 hours.

RPL554 delivered by inhalation as a nebulised solution was well tolerated. Adverse events were generally mild and generally of equal frequency between placebo and active treatment groups. RPL554 produced a rapid bronchodilation in both COPD and asthmatic patients, and increased the provocative concentration of methacholine chloride (PC₂₀MCh) by 1.5 doubling doses compared with placebo (95% confidence interval [CI]: 0.63-2.28; p=0.004). In healthy subjects, RPL554 also produced a significant inhibition of the lipopolysaccharide (LPS)-induced recruitment of the total number of inflammatory cells to the airways (p=0.002), as well as an inhibition of the absolute numbers of neutrophils (p=0.002), eosinophils (p=0.001), lymphocytes (p=0.001) and macrophages (p=0.04) in sputum.

RPL554 has subsequently re-formulated in a neutral pH phosphate buffered suspension formulation for nebulisation. This suspension formulation has been tested in three completed clinical studies:

1.2 Summary of Risks and Benefits

Data from non-clinical studies suggest a potential for hypotension and tachycardia. However, RPL554 has been administered to over 240 subjects in clinical studies to date and has been well tolerated in moderate-severe COPD patients, healthy subjects, asthmatics and allergic rhinitics. No SAEs have been reported with RPL554 to date. The most common adverse events that have been reported at least twice in subjects who have received single or multiple doses of the nebulised suspension of RPL554 were generally mild and in descending order of frequency are headache, cough, dizziness, and palpitations. Adverse events for single and multiple dose studies are summarised in Investigator's Brochure Section 6.3.

The suspension formulation of RPL554 is pH balanced, and has favourable non-clinical toxicology and pharmacokinetic data. There were no effects on embryo-foetal survival and development in the rat. In the rabbit there was an effect on implantation at the highest dose tested which could be related to a pharmacological effect of RPL554, however there was no effect on embryo-foetal survival and development.

There has been no evidence of significant adverse events related to the cardiovascular or gastrointestinal systems, except associated with an increase in heart rate at high doses (12 mg to 24 mg). These small increases in heart rate may relate to the PDE3 inhibitory activity of the compound. In single dose studies there appears to be an increase in the rate of headache, which is most pronounced at doses over 6 mg. There was no other apparent dose related adverse events, with the exception of palpitations in patients dosed at 24 mg. Results from multiple dose data in patients with COPD suggests a transient increase in dizziness, the majority of which occurred during spirometry or dosing; otherwise, the rate of adverse events was similar in RPL554 and placebo treated patients. There was an apparent increase in mild adverse events in healthy subjects treated with high doses of RPL554, which may be associated with the higher serum levels in healthy subjects than in those with obstructive lung disease.

As RPL554 is currently planned to be administered for only 3 days (five doses) in this study, any benefit to the patients will be restricted to the immediate short-term.

2 **OBJECTIVES**

2.1 **Primary Objective**

To investigate the bronchodilator effect on peak FEV_1 (measured in first 4 hours after dosing) and average (measured as the AUC) FEV_1 over 12 hours of nebulised RPL554 dosed twice daily for 3 days (five total doses), as compared to placebo, when administered in addition to once daily tiotropium.

2.2 Secondary Objectives

- To investigate the effect of twice daily nebulised doses of RPL554, as compared to placebo, when administered in addition to tiotropium on lung volumes
- To assess the bronchodilator effect on peak FEV₁ (measured in first 4 hours after dosing) and average (measured as the AUC) FEV₁ over 12 hours of nebulised RPL554 after the first dose as compared to placebo, when administered in addition to tiotropium
- To analyse plasma concentrations and assess the steady state pharmacokinetics of RPL554 when administered in addition to tiotropium
- To assess the tolerability and safety of twice daily nebulised doses of RPL554 in addition to tiotropium
- To assess the dose response of two different doses of RPL554 on peak, average (0 to 12 hours), and morning trough FEV_1 on Day 3 when dosed in addition to tiotropium
- To determine the onset of action of RPL554 when administered with tiotropium (after the first dose)
- To investigate the bronchodilator effect of nebulised RPL554, or placebo, administered in addition to tiotropium on average FEV₁ over 4 hours after each morning dose
- To investigate the effects of RPL554 on specific airway conductance (sG_{aw}) and lung volumes (residual volume [RV], functional residual capacity [FRC]) when administered in addition to tiotropium

2.3 Exploratory Objectives

- To examine the effect of RPL554 on top of tiotropium on average FEV₁ over 24 hours after 3 days of dosing
- To assess morning trough FEV₁ prior to the final dose of study treatment

3 INVESTIGATIONAL PLAN

3.1 **Overall Study Design and Plan Description**

This is a Phase IIb, randomised, double blind, placebo controlled, complete block three way crossover study to investigate treatment with nebulised RPL554 and tiotropium together in patients with moderate to severe COPD. It is planned to randomise up to 30 patients to have 24 evaluable patients at one study centre. The study comprises the following shown in Figure 1: screening, three treatment periods each lasting 3 days and an end of study visit. The procedures performed at each visit are summarised in Section 6 and the study assessments are described in Section 7.

Patients will be screened for eligibility, including a reversibility test with salbutamol between 7 and 21 days before the first dose of study treatment.

Eligible patients will then attend for three separate treatment periods (Treatment Periods 1 to 3) which each last 3 days and are separated by a 7 to 21 day washout period (taken from last dose of study treatment). Patients will be randomised pre-dose at Day 1 of Treatment Period 1. During each treatment period, patients will be present at the study centre from the morning of Day 1 until the morning of Day 4, although they will be able to leave the facility at the discretion of the study centre personnel. Overnight residency is not required except on Day 3 of each treatment period.

In each treatment period, patients will receive an open label dose of tiotropium from a dry power inhaler (DPI) followed immediately (starting within 2 minutes) by a double blind dose of either RPL554 or placebo (depending on treatment sequence) from a nebuliser in the morning on Day 1, Day 2 and Day 3. The dose of RPL554 or placebo will be repeated in the evening on Day 1 and Day 2; there will not be an evening dose on Day 3.

The assessments performed in each treatment period will be the same. Lung function (FEV₁) and forced vital capacity [FVC]) will be measured by spirometry pre-dose and up to 12 hours post-dose on Day 1, up to 4 hours post-dose on Day 2 and up to 24 hours post-dose on Day 3 (i.e. Day 4). Whole body plethysmography will be performed pre-dose on Days 1 and 2 of each treatment period, and 1.25 hours after dosing on Day 2. Vital signs will be measured pre-dose and up to 4 hours post-dose on Day 1, up to 12 hours post-dose on Day 2 and up to 24 hours post-dose on Day 3 (i.e. Day 4). 12-lead electrocardiograms (ECGs) will be

performed pre-dose and up to 4 hours post-dose on Day 1, at 2 hours post-dose on Day 2 and up to 24 hours post-dose on Day 3 (i.e. Day 4). Adverse events will be recorded throughout the study.

Patients will be discharged from the study centre on the morning of Day 4, and after Treatment Period 3 will then attend an end of study visit between 4 and 10 days later.

Study treatment administration, pharmacodynamics, safety and tolerability assessments will be performed whilst patients are resident at the study centre. This is to ensure standardised conditions for dosing and other study procedures. The pre-dose FEV_1 on Day 1 of both Treatment Period 2 and Treatment Period 3 must be within $\pm 20\%$ of the pre-dose FEV_1 on Day 1 of Treatment Period 1 in order to ensure consistent baseline FEV_1 for each study treatment. If the FEV_1 is greater than 20% different then the start of the treatment period must be rescheduled.

3.3 Planned Duration of the Study

The approximate planned duration for each patient could be up to 82 days: 7 to 21 days screening, up to 9 days treatment (three treatment periods of 3 days each separated by 7 to 21 days, taken from last dose of study treatment) and an end of study visit 4 to 10 days after the last treatment visit (Day 4 of Treatment Period 3).

Repeat, rescheduled and unscheduled visits are permitted at the discretion of the Investigator.

3.4 Definition of the End of the Study

The end of the study is defined as the date of the last end of study visit of the last patient in the study.

4 SELECTION OF STUDY POPULATION

The population to be recruited into this study is stable patients with moderate to severe COPD and without significant heart disease. It is expected that current smokers will not comprise more than half the study population.

4.1 Inclusion Criteria

- 1. Sign an informed consent document indicating they understand the purpose of and procedures required for the study and are willing to participate in the study.
- 2. Male or female aged between 40 and 75 years inclusive, at the time of informed consent.
- 3. If male: must agree to meet the following from the first dose up to 2 months after the last dose of study treatment:
 - Not donate sperm
 - *Either:* be sexually abstinent in accordance with a patient's usual and preferred lifestyle (but agree to abide by the contraception requirements below should their circumstances change)

Or: use a condom with all sexual partners. If the partner is of childbearing potential the condom must be used with spermicide and a second highly effective form of contraception must also be used (as defined in Section 8.4)

- 4. If female: either be:
 - a) Of non-childbearing potential defined as being:
 - *Either:* post-menopausal (being spontaneously amenorrhoeic for at least 1 year with an appropriate clinical profile [e.g. age appropriate, history of vasomotor symptoms]
 - *Or:* permanently sterilised e.g. tubal occlusion, hysterectomy, bilateral oophorectomy, bilateral salpingectomy
 - b) Of childbearing potential and agreeing to use a highly effective method of contraception (as defined in Section 8.4) until completion of the end of study visit.
- 5. Have a 12-lead ECG recording at screening and randomisation (pre-dose in Treatment Period 1) showing the following:
 - Heart rate between 45 and 90 beats per minute (bpm)
 - QT interval corrected for heart rate using Fridericia's formula (QTcF) ≤450 msec for males and ≤470 ms for females
 - QRS interval ≤ 120 msec
 - No clinically significant abnormalities (as judged by the Investigator) including morphology (e.g. left bundle branch block, atrio-ventricular nodal dysfunction, ST segment abnormalities)
- 6. Have a screening Holter report with a minimum of 18 hours recording that is able to be evaluated for rhythm analysis which shows no abnormality which indicates a

significant impairment of patient safety or which may significantly impairs interpretation in the opinion of the Investigator including:

- Significant arrhythmias including atrial flutter, atrial fibrillation, ventricular tachycardia
- Any symptomatic arrhythmia (except isolated extra systoles)
- Any sustained second or third degree heart block
- 7. Capable of complying with all study restrictions and procedures including ability to use the study nebuliser and HandiHaler® DPI correctly.
- 8. Body mass index (BMI) between 18 and 33 kg/m² (inclusive) with a minimum weight of 45 kg.
- 9. COPD diagnosis: Patients with a diagnosis of COPD as defined by the American Thoracic Society (ATS)/European Respiratory Society (ERS) guidelines (Celli and MacNee, 2004) with symptoms compatible with COPD for at least 1 year prior to screening.
- 10. Post-bronchodilator (four puffs of salbutamol) spirometry at screening:
 - Post-bronchodilator FEV_1/FVC ratio of ≤ 0.70
 - Post-bronchodilator $FEV_1 \ge 40$ % and $\le 80\%$ of predicted normal
 - Demonstrates ≥ 150 mL increase from pre-bronchodilator FEV₁
- 11. Clinically stable COPD in the 4 weeks prior to screening and randomisation (pre-dose in Treatment Period 1).
- 12. A chest X-ray (post-anterior) at screening, or in the 12 months prior to screening showing no abnormalities, which are both clinically significant and unrelated to COPD.
- 13. Meet the concomitant medication restrictions and be expected to do so for the rest of the study.
- 14. Smoking history of ≥ 10 pack years.
- 15. Capable of withdrawing from long acting bronchodilators for the duration of the study, and short acting bronchodilators for 8 hours prior to spirometry.

4.2 Exclusion Criteria

- 1. A history of life-threatening COPD exacerbation including Intensive Care Unit admission and/or requiring intubation.
- 2. COPD exacerbation requiring oral steroids, or lower respiratory tract infection requiring antibiotics, in the 3 months prior to screening or randomisation (pre-dose in Treatment Period 1).
- 3. A history of one or more hospitalisations for COPD in the 12 months prior to screening or randomisation (pre-dose in Treatment Period 1).
- 4. Lactation (female patients only).
- 5. Positive urine or serum pregnancy test at screening, or a positive urine pregnancy test prior to randomisation (female patients of childbearing potential only).
- 6. Known hypersensitivity to RPL554 or its components.
- 7. Intolerance or hypersensitivity to tiotropium.
- 8. Evidence of cor pulmonale.
- 9. Other respiratory disorders: Patients with a current diagnosis of asthma, active tuberculosis, lung cancer, bronchiectasis, sarcoidosis, lung fibrosis, interstitial lung

diseases, sleep apnoea, known alpha-1 antitrypsin deficiency or other active pulmonary diseases.

- 10. Previous lung resection or lung reduction surgery.
- 11. Use of oral COPD medications (e.g. oral steroids, theophylline and romifulast) in the 3 months prior to screening or randomisation (pre-dose in Treatment Period 1).
- 12. History of, or reason to believe, a patient has drug or alcohol abuse within the past 3 years.
- 13. Inability to perform technically acceptable spirometry or whole body plethysmography (at screening or randomisation [pre-dose in Treatment Period 1])
- 14. Received an experimental drug within 30 days or five half-lives, whichever is longer.
- 15. Patients with a history of chronic uncontrolled disease including, but not limited to, endocrine, active hyperthyroidism, neurological, hepatic, gastrointestinal, renal, haematological, urological, immunological, or ophthalmic diseases that the Investigator believes are clinically significant.
- 16. Documented cardiovascular disease: arrhythmias, angina, recent or suspected myocardial infarction, congestive heart failure, a history of unstable, or uncontrolled hypertension, or has been diagnosed with hypertension in the 3 months prior to screening or randomisation.
- 17. Concurrent use of non-cardioselective oral beta-blockers.
- 18. Has had major surgery, (requiring general anaesthesia) in the 6 weeks prior to screening or randomisation (pre-dose in Treatment Period 1), or will not have fully recovered from surgery, or planned surgery through the end of the study.
- 19. A disclosed history or one known to the Investigator, of significant non-compliance in previous investigational studies or with prescribed medications.
- 20. Requires oxygen therapy, even on an occasional basis.
- 21. Clinically significant prostatic hyperplasia (judged by the Investigator) or bladder-neck obstruction or with narrow-angle glaucoma.
- 22. Any other reason that the Investigator considers makes the patient unsuitable to participate.

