5.10 Rescue Medications

Standard procedures for emergency care should be followed for any individual adverse event, whenever clinically needed (decision to be taken by the Investigator). Short acting bronchodilators (e.g. salbutamol, ipratropium or Combivent) may be used as rescue medication. Rescue medication (salbutamol and ipratropium) will be sourced by the study centre and both will be dispensed at the screening visit. Salbutamol should be considered the primary rescue medication and ipratropium secondary.

Rescue medication use during each treatment period must be separately documented on the eCRF (medication, dose, route, date and time of each administration). Protocol procedures must still continue even if rescue medication has been taken. Salbutamol is to be used for primary rescue use.

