15 APPENDICES

15.1 **Instructions for Tiotropium Use**

HIGHLIGHTS OF PRESCRIBING INFORMATION These highlights do not include all the information needed to use SPIRIVA HANDIHALER safely and effectively. See full prescribing information for SPIRIVA HANDIHALER.

SPIRIVA® HANDIHALER® (tiotropium bromide inhalation powder), for oral inhalation use Initial U.S. Approval: 2004

-INDICATIONS AND USAGE-SPIRIVA HANDIHALER is an anticholinergic indicated for the long-term, once-daily, maintenance treatment of bronchospasm associated with chronic obstructive pulmonary disease (COPD), and for reducing COPD exacerbations (1)

--DOSAGE AND ADMINISTRATION-For oral inhalation only. DO NOT swallow SPIRIVA capsules. Only use SPIRIVA capsules with the HANDIHALER device (2)

Two inhalations of the powder contents of a single SPIRIVA capsule (18 mcg) once daily (2)

---DOSAGE FORMS AND STRENGTHS-Inhalation powder: SPIRIVA capsules contain 18 mcg tiotropium powder for use with HANDIHALER device (3)

---CONTRAINDICATIONS---Hypersensitivity to tiotropium, ipratropium, or any components of SPIRIVA capsules (4)

---WARNINGS AND PRECAUTIONS-

- Not for acute use: Not a rescue medication (5.1)
- Immediate hypersensitivity reactions: Discontinue SPIRIVA
 - HANDIHALER at once and consider alternatives if immediate hypersensitivity reactions, including angioedema, bronchospasm, or

FULL PRESCRIBING INFORMATION: CONTENTS*

- INDICATIONS AND USAGE
- DOSAGE AND ADMINISTRATION DOSAGE FORMS AND STRENGTHS
- 3
- CONTRAINDICATIONS
- WARNINGS AND PRECAUTIONS
 - Not for Acute Use
 Immediate Hypersensitivity Reactions
 Paradoxical Bronchospasm

 - 5.4
 - Worsening of Narrow-Angle Glaucoma
 - 5.5 Worsening of Urinary Retention
- 5.6 Renal Impairment
- ADVERSE REACTIONS
- 6.1 Clinical Trials Experience 6.2 Postmarketing Experience
- DRUG INTERACTIONS
- 7.1 Sympathomimetics, Methylxanthines, Steroids 7.2 Anticholinergics USE IN SPECIFIC POPULATIONS
- 8.1 Pregnancy

anaphylaxis, occur. Use with caution in patients with severe hypersensitivity to milk proteins. (5.2)

- Paradoxical bronchospasm: Discontinue SPIRIVA HANDIHALER and
- consider other treatments if paradoxical bronchospasm occurs (5.3) Worsening of narrow-angle glaucoma may occur. Use with caution in patients with narrow-angle glaucoma and instruct patients to consult a physician immediately if this occurs. (5.4)

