- Worsening of urinary retention may occur. Use with caution in patients with prostatic hyperplasia or bladder-neck obstruction and instruct patients to consult a physician immediately if this occurs. (5.5)

---ADVERSE REACTIONS-

The most common adverse reactions (>5% incidence in the 1-year placebocontrolled trials) were upper respiratory tract infection, dry mouth, sinusitis, pharyngitis, non-specific chest pain, urinary tract infection, dyspepsia, and rhinitis (6.1)

To report SUSPECTED ADVERSE REACTIONS, contact Boehringer Ingelheim Pharmaceuticals, Inc. at [contact] or [contact] TTY, or FDA at [name] or www.fda.gov/medwatch.

--- DRUG INTERACTIONS Anticholinergics: May interact additively with concomitantly used anticholinergic medications. Avoid administration of SPIRIVA HANDIHALER with other anticholinergic-containing drugs. (7.2)

-- USE IN SPECIFIC POPULATIONS Patients with moderate to severe renal impairment should be monitored closely for potential anticholinergic side effects (2, 8.6)

See 17 for PATIENT COUNSELING INFORMATION and FDAapproved patient labeling.

Revised: 1/2016

- 8.2 Labor and Delivery
- 8.3 Nursing Mothers
- 8.4 Pediatric Use
- 8.5 Geriatric Use
- 8.6 Renal Impairment 8.7 Hepatic Impairment 10 OVERDOSAGE
- 11 DESCRIPTION
- 12 CLINICAL PHARMACOLOGY
 - 12.1 Mechanism of Action 12.2 Pharmacodynamics

 - 12.3 Pharmacokinetics
- 13 NONCLINICAL TOXICOLOGY
- 13.1 Carcinogenesis, Mutagenesis, Impairment of Fertility
- 14 CLINICAL STUDIES
- 16 HOW SUPPLIED/STORAGE AND HANDLING 17 PATIENT COUNSELING INFORMATION

*Sections or subsections omitted from the full prescribing information are not listed

FULL PRESCRIBING INFORMATION

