4 CONTRAINDICATIONS

SPIRIVA HANDIHALER is contraindicated in patients with a hypersensitivity to tiotropium, ipratropium, or any components of this product [see Warnings and Precautions (5.2)]. In clinical trials and postmarketing experience with SPIRIVA HANDIHALER, immediate hypersensitivity reactions, including angioedema (including swelling of the lips, tongue, or throat), itching, or rash have been reported [see Warnings and Precautions (5.2)].

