5.4 Worsening of Narrow-Angle Glaucoma

SPIRIVA HANDIHALER should be used with caution in patients with narrow-angle glaucoma. Prescribers and patients should be alert for signs and symptoms of acute narrow-angle glaucoma (e.g., eye pain or discomfort, blurred vision, visual halos or colored images in association with red eyes from conjunctival congestion and corneal edema). Instruct patients to consult a physician immediately should any of these signs or symptoms develop.

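### Exclusion 7 omits ipratropium hypersensitivity, which the protocol's own appended tiotropium label contraindicates, although ipratropium is dispensed at screening

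*Protocol*

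**What the plan says.** Two of the 22 exclusion criteria in Protocol Section 4.2 concern hypersensitivity. Criterion 6 covers RPL554 and its components. Criterion 7 covers "Intolerance or hypersensitivity to tiotropium". The list ends with a general clause, criterion 22: "Any other reason that the Investigator considers makes the patient unsuitable to participate".

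The protocol reproduces the prescribing information for the tiotropium product as Section 15.1. Section 4 of that label states: "SPIRIVA HANDIHALER is contraindicated in patients with a hypersensitivity to tiotropium, ipratropium, or any components of this product". The highlights at the front of the label repeat the same three items.

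Tiotropium 18 mcg once daily is part of all three treatment combinations (Table 1, Section 5.1). Section 5.10 adds: "Rescue medication (salbutamol and ipratropium) will be sourced by the study centre and both will be dispensed at the screening visit". Salbutamol is the first-choice rescue drug and ipratropium the second. Section 5.9.1 also lets the investigator move patients who stop long-acting bronchodilators on to short-acting ones, with ipratropium among the examples. Outside the 3-day treatment periods that use may be on a regular schedule.

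**The concern.** The eligibility list is narrower than the contraindication printed in the same protocol. Applied as written, it lets through a patient whom the appended label says must not receive the open-label drug given in every period. The rescue provisions then supply that patient with the very drug to which he or she is known to react.

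The omission looks unintended. Criterion 21 excludes "Clinically significant prostatic hyperplasia (judged by the Investigator) or bladder-neck obstruction or with narrow-angle glaucoma". The label treats these three conditions only as cautions: "Use with caution in patients with prostatic hyperplasia or bladder-neck obstruction" and "SPIRIVA HANDIHALER should be used with caution in patients with narrow-angle glaucoma". Three cautions have become fixed exclusions, while one contraindication is left to judgement.

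What is at stake is a first exposure. Section 5.2 of the label lists angioedema, bronchospasm and anaphylaxis among the possible immediate reactions. The stopping rules in Protocol Section 4.3.1 and in that label section act only after a reaction has occurred.

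**Working it through.** There is no figure in the plan to reproduce. The check is a comparison of texts.

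**1. Contraindications against criterion 7**

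| Hypersensitivity contraindicated by label section 4 | Exclusion 7, read literally | Exclusion 7, with tiotropium read as the product |
|---|---|---|
| Tiotropium | covered | covered |
| Ipratropium | not covered | not covered |
| Any component of the product | not covered | covered |
| Total covered | 1 of 3 | 2 of 3 |

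The wider reading is reasonable because only one tiotropium product is used (Section 5.2.2). Ipratropium is uncovered on both readings.

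**2. Whether another criterion fills the gap**

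There are 15 + 22 = 37 criteria, and 0 of 37 name ipratropium. The nearest candidates are:

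- Exclusion 6: RPL554 and its components only.
- Exclusion 15: chronic uncontrolled disease, including immunological disease, that the investigator finds clinically significant. A drug hypersensitivity is not such a disease.
- Inclusions 7 and 13: ability to comply with procedures, and concomitant medication restrictions. Neither concerns hypersensitivity.
- Exclusion 22: could apply, but only if the investigator learns of the reaction and judges it relevant.

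**3. Whether another section fills the gap**

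- The body of the protocol refers to Section 15.1 in Sections 5.2.2, 5.4.2.2 and 5.5, for use of the inhaler and storage. No eligibility criterion refers to it.
- Section 7.1.6 confirms eligibility against the inclusion and exclusion criteria. Section 6.2 gives a randomisation number to patients who still meet them.
- Section 7.1.2 records active conditions, surgery and prior respiratory therapies. Section 5.9.1 records COPD therapies from the 3 months before first dosing. Neither asks expressly for drug-allergy history, so an older reaction to ipratropium might not come up.

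**4. Exposure if such a patient enters**

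- Tiotropium: 3 periods × 3 once-daily doses = 9 doses for a patient who completes the study.
- Ipratropium: in the patient's hands from screening, which is 7 to 21 days before the first supervised tiotropium dose.

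**The case against.** The strongest reply is that the information is not missing. The label is part of the protocol and prints the contraindication twice. A physician who knew of an ipratropium reaction would be expected to use criterion 22, which exists for unlisted reasons of this kind. History and prior respiratory therapies are taken at screening, and eligibility is checked again before the first dose. Nobody is obliged to take ipratropium: salbutamol comes first, and the replacement for a long-acting drug is the investigator's choice. Tiotropium is given at the centre by trained staff, with provision for emergency care. Excluding three label cautions in criterion 21 is permissible conservatism and does not itself create an error.

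Much of this stands as a limit on the size of the point. The risk is small, exposure to ipratropium is possible rather than certain, and the contrast with criterion 21 suggests an oversight without adding a second defect. The count of covered contraindications measures wording, not risk. The component wording is only a clarification.

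The reply does not close the gap. The appendix is cited for inhaler use and storage, eligibility is decided on the numbered criteria, and no section prompts the question that would bring the reaction to light. Reliance on criterion 22 would make criteria 6, 7 and 21 equally unnecessary, yet those are written out.

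**Conclusion.** The concern holds. Exclusion 7 leaves out ipratropium hypersensitivity, a contraindication in the protocol's own appendix. Within the eligibility list, only the discretionary criterion 22 covers such a patient.

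The point is one of patient safety and does not touch sample size, type I error or the analysis. The documents give no prevalence of ipratropium hypersensitivity. An assumed range of 0 to 1 patient among up to 30 randomised is a judgement, not a derived figure, and the conclusion does not depend on it. It rests on the wording alone: a written eligibility rule conflicts with a written contraindication, and the correction is cheap enough to be worth making even if no such patient ever presents.

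**What to change.** Extend exclusion 7 so that intolerance or hypersensitivity to ipratropium, or to any component of the tiotropium product, excludes a patient in the same way as a reaction to tiotropium. Use identical wording in the eligibility checks at screening and before dosing on Day 1 of Treatment Period 1, so that the question is put to every patient.

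The ipratropium wording is the substantive change. The component wording makes explicit what the present text can already be read to mean. One detail needs a decision: label section 5.2 advises only caution in severe milk-protein hypersensitivity, so the sponsor's medical monitor should confirm how the component wording applies to such patients.

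The cost is one line in a protocol amendment and one line in the eligibility checklist, with no new procedure. Section 11.2 requires the reason for a change to be documented, and ethical and regulatory approval if the amendment is substantial; the sponsor would have to classify this one. The only effect on recruitment is at most a rare extra screen failure. A checklist line pointing to the label's contraindications could serve in the interim, but it would leave the criterion itself out of step with the label.
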